5. ANALYSIS SETS

5.1. **Definition**

Two cohorts will be defined for the purpose of the analysis: the Exposed Set (ES) and the Per-protocol set (PPS) for analysis of immunogenicity. All analyses will be performed per treatment actually administered.

5.1.1. **Exposed Set (ES)**

The ES will include all subjects with study vaccine administration documented.

- A **safety** analysis based on the ES will include all vaccinated subjects.
- An **immunogenicity** analysis based on the ES will include all vaccinated subjects for whom immunogenicity data are available.

5.1.2. **Per-protocol set (PPS) for analysis of immunogenicity**

The PPS for immunogenicity will be defined by time-point (Day 8, Day 31, Day 61 and Day 91) and will include all vaccinated subjects:

- Meeting all eligibility criteria (i.e. no protocol violation linked to the inclusion/exclusion criteria, including age);
- Who received the study vaccine according to protocol procedures;
- Who did not receive a concomitant vaccination/medication/product leading to elimination from the PPS analysis up to the corresponding time-point as described in Section 6.6 of the protocol;
- Who did not present with an intercurrent medical condition leading to elimination from the PPS analysis up to the corresponding time-point, as described in Section 6.7 of the protocol;
- Who complied with the post-vaccination immunogenicity blood sampling schedule at the corresponding time-point, as specified in [Table 2](#) of the SAP;
- For whom post-vaccination immunogenicity results are available for at least 1 assay at the corresponding time-point.
- The intervals allowed for the inclusion in the PPS for analysis of immunogenicity as specified in [Table 2](#) of the SAP as below:

Table 2 Intervals between study visits

	Interval	Optimal length of interval	Allowed interval for PPS immunogenicity
Interval to be considered for enrollment	DOB → Visit 1 (Day 1)	18-45 years	18-45 years
	SCR – Visit 1 (Day 1)	0-7 days	0-7 days
Interval to be considered for blood sampling	Visit 1 (Day 1) → Visit 2 (Day 8)	7 days	7 - 10 days
	Visit 1 (Day 1) → Visit 3 (Day 31)	30 days	30 - 45 days
	Visit 1 (Day 1) → Visit 4 (Day 61)	60 days	56 – 70 days
	Visit 1 (Day 1) → Visit 5 (Day 91)	90 days	86 - 100 days

When presenting different time-points, the PPS for immunogenicity will be adapted for each time-point (Day 8, Day 31, Day 61 and Day 91).

5.2. Criteria for eliminating data from Analysis Sets

Elimination codes are used to identify subjects to be eliminated from analysis. Details are provided below for each set.

5.2.1. Elimination from Exposed Set (ES)

Code 1030 (Study vaccine not administered at all) and code 900 (invalid informed consent or fraud data) will be used for identifying subjects eliminated from ES.

5.2.2. Elimination from Per-protocol analysis Set (PPS)

5.2.2.1. Excluded subjects

A subject will be excluded from the PPS analysis under the following conditions:

Code	Condition under which the code is used
900	Invalid informed consent or fraud data (Subjects receiving a code 900 should not receive any other elimination codes)
1030	Study vaccine not administered at all (Subjects receiving a code 1030 should not receive any other elimination codes)
1050	Randomization failure (subject not randomized in the correct group) Comment: To check for manual randomisation, treatment not compatible with one assigned by SBIR
1060	Randomization code was broken
1070**	Study vaccine dose not administered according to protocol Incorrect volume of the vaccine given Administration not according to protocol for reason specified by the investigator, other than side, site and route Site of the injection of vaccine is wrong or unknown Route of the study vaccine is wrong or unknown Wrong reconstitution of administered vaccine
1080	Vaccine temperature deviation
1090	Expired vaccine administered
2010	Protocol violation (inclusion/exclusion criteria including age) SCR – VIST 1 – 0-7 days# DOB – VISIT 1 – 18-45 years

*Attribution of these elimcodes to subject need CRDL review of individual listing

** Attribution of code 1070 to a subject requires CRDL confirmation

need to be confirmed in the Pre-analysis meeting

5.2.2.2. Right censored Data

- Data from a subject will be censored from visit x for the PPS analysis under the following conditions. The code ****.Vx will be used to identify subjects whose immunogenicity data should be eliminated from a specific visit onwards. For Day 8, Day 31, Day 61 and Day 91 PP, the information will be checked from vaccination up to Day 7, Day 30, Day 60 and Day 90, respectively.

- The code ****.Vx+ will also be used to identify study withdrawal.

1040.Vx+*	Administration of concomitant vaccine(s) forbidden in the protocol 
 Use of any investigational or non-registered product (drug or vaccine) other than the study vaccine up to study completion (Contact 1 [Day 181]) A vaccine not foreseen by the study protocol administered during 30 days following vaccination, with the exception of seasonal influenza vaccine which may be administered ≥ 15 days after the dose of study vaccine. (To note – this code will only be checked at Day 8 and Day 31 PP and will be carried forward for D61 and D91 PPS)
2040.Vx+*	Administration of any medication forbidden by the protocol 
 Any investigational or non-registered product (drug) other than the study vaccines used during the study period. Immunoglobulins and/or any blood products administered up to 90 days post study vaccination. Immunosuppressants or other immune-modifying drugs administered chronically (i.e. more than 14 days in total) or any long-acting immune-modifying drugs (e.g. infliximab) administered any time up to 90 days post-vaccination. For corticosteroids, this will mean ≥ 5mg/day prednisone or equivalent.
2050.Vx+*	Intercurrent medical condition 
 Intercurrent medical condition (up to Day 91/Visit 5) that has the capability of altering immune response which may influence immune response
2070.Vx+*	Concomitant infection which may influence immune response
2071.Vx+	Withdrawal from the study impacting PPS

*Attribution of these elimcodes to subject need CRDL review of individual listing

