5.2.2.3. Visit-specific censored Data

Data from visit x will be censored for the PPS analysis under the following conditions.

Code	Condition under which the code is used
2090.Vx	Subjects did not comply with blood sample schedule Applicable visits 
 For Day 8 PP, to check for DOSE to DAY 8 BS = 7-10 days For Day 31 PP, to check for DOSE to DAY 31 BS = 30-45 days For Day 61 PP, to check for DOSE to DAY 61 BS = 56-70 days For Day 91 PP, to check for DOSE to DAY 91 BS = 86-100 days
2100.Vx	Serological results not available post-vaccination \rightarrow No immunological result at all for the specific blood sample collection timepoint Comment: - To check for availability of RSV-A neutralising antibody and/or RSVPreF3 IgG antibody result at each applicable PPS timepoint
2120.Vx	Obvious incoherence or abnormality or error in immunogenicity (antibody) data*** To check on RSV-A neutralising antibody and RSVPreF3 IgG antibody result at each applicable PPS timepoint

*** Elimination criteria for implausible RSV serum immune responses (neut and/or ELISA): More than 4-fold decrease from pre-vaccination to Day 30; After Day 30, more than 4-fold increase or more than 8 fold decrease within a 30 day period

5.3. **Important protocol deviation not leading to elimination from per-protocol analysis set**

The following important protocol deviations will be reported by groups:

- Forced randomization: In case of supplies shortage for the next assigned vaccine according to the randomization schedule at the clinical site, the randomization system will use the forced randomization procedure in order to continue to enrol and vaccinate subjects. The system moves seamlessly to the next treatment/randomization number for which vaccine supplies are available. The site will not be aware of the forced randomization event.
- Manual randomization: In case the randomization system is unavailable, the investigator has the option to request randomization to the SBIR helpdesk.
- Short follow-up: subjects who completed the last study contact before the minimum length of follow-up requirement.

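### PPS exclusion checks stop at nominal Days 7/30/60/90 rather than at the actual blood draw, and the code 1040 note leaves investigational vaccines unchecked after Day 30 (minor)

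*SAP*

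**What the plan says.** SAP 5.2.2.2 lists the codes that remove a subject's immunogenicity data from a given visit onwards: 1040 (concomitant vaccine), 2040 (medication), 2050 (intercurrent condition), 2070 (concomitant infection) and 2071 (withdrawal). For the four per-protocol sets, "the information will be checked from vaccination up to Day 7, Day 30, Day 60 and Day 90, respectively".

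SAP 5.2.2.3 sets the sampling windows. The rule for the Day 31 set reads "For Day 31 PP, to check for DOSE to DAY 31 BS = 30-45 days". The other three sets have the same kind of rule, with windows of 7-10 days (Day 8), 56-70 days (Day 61) and 86-100 days (Day 91). SAP Table 2 gives the same intervals.

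Code 1040 has two bullets. The first is "Use of any investigational or non-registered product (drug or vaccine) other than the study vaccine up to study completion (Contact 1 [Day 181". The second covers vaccines not foreseen by the protocol, for 30 days after the dose, with an allowance for influenza vaccine. A note in the same entry says "this code will only be checked at Day 8 and Day 31 PP and will be carried forward for D61 and D91 PPS". Code 2040 repeats the investigational-product bar for drugs only. It also covers immunoglobulins, blood products and immune-modifying drugs up to 90 days after vaccination. Code 2050 runs to Day 91/Visit 5.

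Protocol 6.6.2 lists investigational or non-registered drugs and vaccines, up to Day 181, among the products that may make a subject non-evaluable for the PPS.

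**The concern.** Whether a sample belongs in the PPS should depend on what happened before that sample was drawn. A cut-off fixed at the day before the nominal visit gives that result only for subjects sampled on the nominal day. For a late sample it ignores the last days before the draw. For an early sample it counts days after the draw.

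The PPS is the main immunogenicity population. The largest window gap falls at Day 31, the time-point of the planned between-group comparisons and trend tests. Immunoglobulins and immune-modifying drugs are restricted because they can change the measured response, so these are the samples the PPS is meant to leave out.

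The code 1040 note raises a separate problem that does not depend on a late visit. A product class that the code itself bars to Day 181 is no longer looked for after Day 30.

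**Working it through.** **Inputs.** The cut-offs are Days 7, 30, 60 and 90 (SAP 5.2.2.2). The windows are 7-10, 30-45, 56-70 and 86-100 days after the dose (SAP 5.2.2.3 and Table 2). The day of vaccination is Day 1 (SAP 11.2.1), so a sample taken *d* days after the dose falls on study Day *d* + 1.

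**The plan's cut-offs.** Nominal visit day minus 1: 8 - 1 = 7, 31 - 1 = 30, 61 - 1 = 60, 91 - 1 = 90. The stated cut-offs are therefore the day before each nominal visit.

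**Gap and overrun.** Unchecked full days before the latest allowed draw = (latest sample day - 1) - cut-off. Days still checked after the earliest allowed draw = cut-off - earliest sample day, with a floor of 0.

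| PPS | Allowed sample days | Cut-off | Unchecked before latest draw | Checked after earliest draw |
|---|---|---|---|---|
| Day 8 | 8-11 | 7 | (11 - 1) - 7 = 3 | 0 |
| Day 31 | 31-46 | 30 | (46 - 1) - 30 = 15 | 0 |
| Day 61 | 57-71 | 60 | (71 - 1) - 60 = 10 | 60 - 57 = 3 |
| Day 91 | 87-101 | 90 | (101 - 1) - 90 = 10 | 90 - 87 = 3 |

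**Two cases under the rule as written.**
- Immunoglobulin on Day 35, Day 31 sample on Day 40 (39 days after the dose, in window). The Day 31 check ends on Day 30, so the sample stays in. The Day 61 check finds the event and removes Visits 4 and 5. One sample is wrongly kept.
- Blood product on Day 59, Day 61 sample on Day 57 (56 days after the dose, in window). The check runs to Day 60, so a sample drawn two days before the event is removed.

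**How much of the Day 91 gap is real.** For immunoglobulins, blood products and immune-modifying drugs, the protocol and code 2040 stop at 90 days after vaccination, which is Day 91. Against a cut-off of Day 90, the shortfall is 91 - 90 = 1 day. The 10-day figure applies only to investigational products and, if Visit 5 means the actual visit, to intercurrent conditions.

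**Code 1040.** Its last check ends on Day 30. For an investigational or non-registered vaccine, the unchecked stretch before an on-time Day 61 sample is 60 - 30 = 30 days (Days 31-60). Before an on-time Day 91 sample it is 90 - 30 = 60 days (Days 31-90). For the latest allowed samples it is 70 - 30 = 40 and 100 - 30 = 70 days. Code 2040 does not fill this hole, because its investigational-product bullet names drugs only.

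**Size, by assumption only.** If *m* of 125 subjects in a group each had a titre raised *f*-fold, the group GMT would be multiplied by *f*^(*m*/125). With *m* = 1 and *f* = 2 this is 1.0056. With *m* = 6 and *f* = 4 it is 1.0688. The documents support no particular *m* or *f*.

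**The case against.** The strongest reply is that the rule follows the plan's own definition. SAP 5.1.2 asks for no product "leading to elimination from the PPS analysis up to the corresponding time-point" and defines the time-points as Day 8, 31, 61 and 91. It does not mention the sample date, so a nominal cut-off is a legitimate reading. That stands: a reader might infer that 5.2.2.2 contradicts the PPS definition, but the text does not establish it. The nominal reading still leaves in samples drawn after products that Protocol 6.6.2 and code 2040 list.

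Two other stronger readings also fail. One is that every forbidden product goes unchecked for 10 days at Day 91; for most products the protocol's own restriction ends on Day 91. The other is that ordinary vaccines after Day 30 slip through; the protocol restricts them for 30 days only, so carrying code 1040 forward is correct for them. The note directly follows the 30-day bullet and may have been meant for it alone, but as worded it refers to the whole code.

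Safeguards exist but are partial. Codes 1040, 2040, 2050 and 2070 need review of individual listings by the clinical research lead, but no written rule ties that review to the sample date. Code 2120 removes implausible titres, but from baseline to Day 30 it flags only falls of more than 4-fold, and afterwards only rises above 4-fold or falls above 8-fold within 30 days. The Exposed Set analysis does not help, since it retains the same samples.

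The reply is also right about frequency. On-time samples have no cut-off gap, visits are to be held at the optimal interval where possible, and planned use of investigational products or immunoglobulins is an exclusion criterion. Counting window days says nothing about how many subjects are affected.

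**Conclusion.** The point holds as a minor defect in the PPS rules. As written, they can keep a late Day 8, 31 or 61 sample drawn after a listed product or condition. They can also drop an early Day 61 or Day 91 sample for an event in the 3 days after the draw; this second error cannot occur at Day 8 or Day 31. Under codes 2040, 2050 and 2070 a missed event normally affects one visit, because the next check starts again from vaccination. No later check follows Day 91. The code 1040 hole is narrower in product but longer in time: investigational or non-registered vaccines, Days 31-90 before an on-time Day 91 sample.

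A reader might infer that the immunogenicity results would be materially biased. The documents do not support that. They give no event rates. Between-group comparisons are exploratory and descriptive, collection is observer-blind to Day 91, and the primary safety analysis uses the Exposed Set. Under the assumed range of 1 to 6 affected subjects per 125, with 2- to 4-fold rises, a group GMT would move by about 0.6% to 6.9%. The true figure is probably at the low end or below it.

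The conclusion takes the day arithmetic from SAP 11.2.1 and reads the code 1040 note as covering both bullets.

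**What to change.** In SAP 5.2.2.2, replace the fixed days with a check from vaccination up to the subject's actual blood-sample date for that time-point, or to the end of the protocol's restriction period for that product if earlier. State whether the sampling day itself counts, since the present cut-offs stop the day before the nominal visit. State also whether Visit 5 in code 2050 means nominal Day 91 or the actual visit.

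Limit the code 1040 note to the 30-day vaccine bullet, and check the investigational-product bullet at all four time-points. Ordinary vaccines would be handled as now.

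The cost is a few SAP phrases and one date comparison in the elimination program. No new data are needed, because Protocol 6.6.1 already requires the Section 6.6.2 products to be recorded for their full periods. The change should be made before the Day 91 analysis, when the study statistician is unblinded, so that it cannot look post hoc.

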5.2.2.3. Visit-specific censored Data

Data from visit x will be censored for the PPS analysis under the following conditions.

Code	Condition under which the code is used
2090.Vx	Subjects did not comply with blood sample schedule Applicable visits 
 For Day 8 PP, to check for DOSE to DAY 8 BS = 7-10 days For Day 31 PP, to check for DOSE to DAY 31 BS = 30-45 days For Day 61 PP, to check for DOSE to DAY 61 BS = 56-70 days For Day 91 PP, to check for DOSE to DAY 91 BS = 86-100 days
2100.Vx	Serological results not available post-vaccination \rightarrow No immunological result at all for the specific blood sample collection timepoint Comment: - To check for availability of RSV-A neutralising antibody and/or RSVPreF3 IgG antibody result at each applicable PPS timepoint
2120.Vx	Obvious incoherence or abnormality or error in immunogenicity (antibody) data*** To check on RSV-A neutralising antibody and RSVPreF3 IgG antibody result at each applicable PPS timepoint

*** Elimination criteria for implausible RSV serum immune responses (neut and/or ELISA): More than 4-fold decrease from pre-vaccination to Day 30; After Day 30, more than 4-fold increase or more than 8 fold decrease within a 30 day period

5.3. **Important protocol deviation not leading to elimination from per-protocol analysis set**

The following important protocol deviations will be reported by groups:

- Forced randomization: In case of supplies shortage for the next assigned vaccine according to the randomization schedule at the clinical site, the randomization system will use the forced randomization procedure in order to continue to enrol and vaccinate subjects. The system moves seamlessly to the next treatment/randomization number for which vaccine supplies are available. The site will not be aware of the forced randomization event.
- Manual randomization: In case the randomization system is unavailable, the investigator has the option to request randomization to the SBIR helpdesk.
- Short follow-up: subjects who completed the last study contact before the minimum length of follow-up requirement.

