6.3. Immunogenicity

6.3.1. Analysis of immunogenicity planned in the protocol

The analysis will be performed on the applicable PPS cohort for immunogenicity and, if in any group the percentage of vaccinated subjects with serological results excluded from the PPS for analysis of immunogenicity is $\geq 5\%$, a second analysis will be performed on the ES.

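### Code 2120 removes per-protocol antibody results on the size of the titre change alone, and no full-study analysis that keeps them is guaranteed

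*SAP*

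**What the plan says.** SAP 5.2.2.3 lists reasons for dropping a single visit: "Data from visit x will be censored for the PPS analysis under the following conditions". Code 2120.Vx is labelled "Obvious incoherence or abnormality or error in immunogenicity (antibody) data". Its footnote turns that label into a fold-change limit on either assay: "More than 4-fold decrease from pre-vaccination to Day 30; After Day 30, more than 4-fold increase or more than 8 fold decrease", the later limits applying to changes within 30 days. It asks for no repeat test, sample check or identified error.

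SAP 5.2.2.2 marks the codes for forbidden vaccines, forbidden medication, intercurrent conditions and infection for review of individual listings by the clinical lead (CRDL). Code 2120 has no such mark. Infection has its own code, "Concomitant infection which may influence immune response", which censors from that visit onwards.

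SAP 6.3.1 and Protocol 10.9 analyse immunogenicity on the per-protocol set (PPS). If any group loses 5% or more of its vaccinated subjects with serology, "a second analysis will be performed on the ES". Only codes 900 and 1030 remove anyone from the Exposed Set (ES; SAP 5.2.1), so an ES analysis is free of code 2120. SAP 6.3.2 and 8.1 put the Step 1 Day 31 interim on the ES without condition, for internal use and on data that may not be clean.

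The PPS definitions in Protocol 10.5.2 and SAP 5.1.2 contain no limit on titre change, and SAP section 9 reports no change from the planned analyses.

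**The concern.** Whether a result stays in the main immunogenicity set depends on the result itself, and the arms are not equally exposed to the limits. Placebo women are expected to change little, so to Day 31 they lie much nearer the lower limit than vaccine responders do.

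After Day 30 a sharp rise is what a natural RSV re-infection would look like. Protocol 1.1 says that re-infection happens throughout life and generally goes undiagnosed. The infection code would then miss it, and code 2120 would remove it as implausible. Because the code is visit-specific, such a woman could be dropped at Day 61 and return at Day 91 with her titre still raised.

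At stake are the placebo reference for the Day 31 comparisons and the description of persistence to Day 91 under the secondary objective. Without a full-study table that keeps the flagged values, a reader cannot see whether the rule mattered.

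**Working it through.** **Inputs from the documents.** 125 per group; SD of log10 RSV-A titre about 0.4 (Protocol 10.4); fold limits of 4 (0.602 log10) and 8 (0.903 log10); 5% trigger. **Assumed, because the documents give no figure:** the SD *s* of the placebo pre-to-Day 31 log10 difference (equivalently the pre/post correlation ρ), the vaccine fold rise, and the share of placebo women with a real later rise.

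**1. The plan's own precision.** 1.96 × 0.4 × √(2/125) = 0.099 log10. This reproduces the 0.1 that Protocol Table 20 gives for 1.3- and 2-fold at SD 0.4. As 10^0.1 = 1.26, a between-group ratio is known to within a factor of about 1.26.

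**2. Trigger.** 6/125 = 4.8% and 7/125 = 5.6%. Up to 6 per group (24 of 500) can be excluded, for all reasons together, with no ES analysis.

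**3. Rule to Day 31, placebo with no true change.** With z = 0.602/s, the fraction removed is p = 1 − Φ(z), and the mean log10 fold change rises by d = s·φ(z)/(1 − p). With equal pre and post variance, half of d falls on the Day 31 mean and half on baseline, so the GMT shift is d/2. The baseline-adjusted mean used for the planned ratios shifts by about d(1 + ρ)/2. At SD 0.4, ρ = 1 − (s/0.4)²/2.

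| s | ρ | removed | expected of 125 | fold rise | GMT | adjusted mean |
|---|---|---|---|---|---|---|
| 0.20 | 0.88 | 0.1% | 0.2 | +0.2% | +0.1% | +0.2% |
| 0.25 | 0.80 | 0.8% | 1.0 | +1.3% | +0.6% | +1.2% |
| 0.30 | 0.72 | 2.2% | 2.8 | +3.8% | +1.9% | +3.3% |

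Over a wider range, ρ = 0.9 removes 0.04% (fold rise +0.06%) and ρ = 0.5 removes 6.6% (+13.5%). A vaccine group with an assumed 4-fold rise loses 0.13% at ρ = 0.5 and less at higher ρ. The effect is therefore almost all in placebo, or in vaccinees who do not respond.

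**4. After Day 30.** The SAP does not say which of the two results is flagged; I take the later visit. If a fraction *a* of placebo women have an 8-fold rise in one interval and are otherwise average, removing them multiplies the placebo GMT at that visit by 10^(−0.903a). For a = 0.02 this is 0.959 (−4%); for a = 0.05 it is 0.901 (−10%).

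Noise alone acts in the same direction. In placebo with no true change, the unequal limits remove 2.6% as rises and 0.2% as falls at ρ = 0.7, and 6.6% and 1.2% at ρ = 0.5. In a group that wanes to an assumed 0.7 of its level over the interval, the two sides nearly cancel (mean change +0.1% at ρ = 0.7, +0.3% at ρ = 0.5).

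**5. What can pass unseen.** Suppose six placebo women have a 4-fold fall and the other 119 average no change. The full-group fold rise is 10^(−6 × 0.602/125) = 0.936, against 1.00 with them removed, a 7% difference. With 8-fold falls it is 0.905, a 10% difference. Neither case reaches 5% by itself.

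**The case against.** Several stronger readings are tempting, and the documents do not support them.

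- **A reader might infer that no analysis at all is free of the rule.** The Step 1 interim is on the ES unconditionally. It covers about 60 of 500 subjects, stops at Day 31 and may use unclean data, so it cannot replace a full-study check.
- **The lack of an upper limit to Day 30 might look like a defect.** A large rise by then is the vaccine response under study, and a cap would cut into it.
- **The 8-fold fall limit might be thought to touch only vaccinated women who wane.** Noise can produce such falls in placebo too (1.2% at ρ = 0.5).
- **The 4 to 10% might be applied to both Day 61 and Day 91.** The code is visit-specific. A rise that persists is flagged once, so both visits are affected only if new rises occur in each interval.
- **The 5% trigger might be said usually to fail.** It counts every kind of exclusion in any of four groups, so other reasons may set it off. It also responds to the rule itself: in placebo, this rule alone stays below the trigger with probability 95% at ρ = 0.7 but only 27% at ρ = 0.5, where the distortion is largest.

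It is also fair that exclusions will be visible. SAP Template 4 has a line for incoherent data, and elimination codes and individual results are listed. Safety is primary, and the immunogenicity comparisons are exploratory and described as descriptive (Protocol 10.9.2 and 10.10, SAP section 7). These points limit the consequence. They do not remove it, because counts of exclusions do not show their effect on GMTs or ratios.

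**Conclusion.** The point stands in a limited form. Code 2120 selects on the outcome without a confirmed error, and a full-study analysis that keeps those values depends on a 5% threshold designed for exclusions in general.

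The direction is not uniform, so the documents do not support a claim that the rule favours the vaccine overall. To Day 31 it raises the placebo mean and pulls vaccine/placebo ratios towards 1, if the removed falls are real. After Day 30 it can lower the placebo mean and push ratios away from 1.

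The size is probably small: a shift of 0.2 to 3.8% in placebo fold rise at the assumed SDs of 0.20 to 0.30, about half that in the GMT, and 4 to 10% at one later visit if 2 to 5% of placebo women have an 8-fold rise. All of these lie inside the factor of about 1.26 that the plan accepts as precision. The Day 31 effect becomes material only at low to moderate pre/post correlation and is negligible at 0.9. The correlation and the share with real rises are assumptions that the trial's own data can replace.

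**What to change.** Add to SAP 6.3 that the Day 31, 61 and 91 GMTs/GMCs, fold rises and between-group ratios will always also be presented with code 2120 values kept, whatever the 5% rule gives. Make code 2120 subject to blinded review of existing laboratory and sample records before it is applied, in the way that other codes already go to listing review, and complete that review before the statistician is unblinded for the Day 91 analysis. The same edit should say which visit and which assay a flag removes.

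The cost is one SAP sentence for the tables, one repeat of the main tables, and a short review of the few flagged records. New repeat testing would be extra laboratory work and is not needed for this. The downside is that a few extreme values remain in the sensitivity tables. If the rule rarely acts, the repeat will show that.
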